- h The 3-day practice diary during the Screening Period and the 3-day Baseline diary must both be valid in order to randomize a patient. The trainer/rater will call the patient before the scheduled start of the diary completion periods to remind him or her to keep the PD diary and to review completion instructions. The patient will also be reminded to send the completed practice diary to the trainer/rater and to bring their Baseline diary to the Baseline Visit. If the practice or Baseline diary is invalid, the patient may be retrained and complete another practice or Baseline diary within the 6-week window of the Screening Period, if the patient is otherwise eligible for the study.
- PD diary collected over the 3 consecutive 24-hour periods before the day of the scheduled study visits on Week 2, 6, 12, 18 and 24. The PD diary trainer/rater will call the patient before the scheduled start of the 3-day PD diary completion period (at the latest, on the last working day before the scheduled start of the PD diary completion) and review completion instructions. The patient will also be reminded to bring their PD diary to the visit. The trainer/rater will instruct the patient if the PD diary contains missing and/or invalid entries to reinforce instructions for appropriate completion.
- Done only if the ET date coincides with the scheduled diary collection return date.
- ^k To be collected during patient's ON state.
- Patients will be instructed to take two (2) tablets of the dispensed blinded IMP by mouth twice daily (BID), in the morning and in the evening preferably at the same time each day, for a total of four (4) tablets per day. The evening dose should be approximately 12 hours after the morning dose. Patients will be instructed to take their morning and evening doses at least 1 hour before or 2 hours after a meal and to refrain from eating for at least 1 hour after dosing.

^m Pretreatment AEs.

Confidential Page 35 of 195

Table 1: Part A – Schedule of Events/Evaluations (continued)

TOZ-CL05 PART A: DOUBLE-BLIND PHASE

- ⁿ Hematology tests: Hemoglobin concentration, hematocrit, red blood cell count, total and differential white blood cell, thrombocyte (platelet) count.

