6.2.18 Visit 7 (Week 24) (End of Double-Blind / Start of Open-Label Phase)

Note: Confirm the arrangement for laboratory sample pick-up on the day of the Week 24 visit with the courier (see Central Laboratory Procedures Manual).

Note: If a patient decides to withdraw from study at Week 24, their Week 24 visit will be an Early Termination Visit (see Section 6.2.32) and they will be asked to return for a Safety Follow-Up Visit within 28 ± 3 days (see Section 6.2.35).

- 1. Upon arrival, obtain samples for the following laboratory tests and record the date and time of collection:
 - a. Obtain first PK blood sample for plasma tozadenant concentration. Record the patient-reported date and approximate time when the patient took the most recent dose of IMP. Record the date and time of PK sample collection.

- For patients concomitantly taking pramipexole, plasma will also be analyzed for pramipexole plasma concentration using the same PK blood sample as drawn for tozadenant PK. Record the patient-reported date and approximate time when the patient took the previous dose of pramipexole prior to sampling. See Section 8.2.
- b. Hematology and chemistry (including liver function tests).
- c. TSH, free T3, and free T4.
- d. Urine sample for urinalysis.
- e. Verify method of contraception has not changed since the previous visit. For females of childbearing potential: urine pregnancy test.

- 2. Review the patient's PD diary recordings for the 3 consecutive days (i.e., 3 consecutive 24-hour periods) directly preceding this visit, and address any illegible or unclear entries.
- 3. Assess AEs by asking open-ended queries and record the assessments.
- 4. Record concomitant medication use; assess and record any changes to anti-PD medication dose or regimen.
- 5. Obtain and record BP and pulse measurements after at least 5 minutes supine rest and again after standing for approximately 1 and 3 minutes.
- 6. Obtain 12-lead ECG and ensure the ECG is collected at a time when the patient is not experiencing dyskinesia that would interfere with an adequate recording. Assess any changes from Baseline for clinical significance.
- 7. Obtain weight.
- 8. Record the date and approximate time of the most recent dose of levodopa taken prior to the UPDRS assessment.
- 9. Perform the following assessments in the ON state (items a, b and c):

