6.2.32 Early Termination Visit – Part A (Weeks 0–24)

Note: Confirm the arrangement for laboratory sample pick-up on the day of patient's Early Termination Visit with the courier (see Central Laboratory Procedures Manual).

If the patient has discontinued IMP, perform this visit as soon as possible after the last dose of IMP. If the patient took the last dose of IMP 28 or more days prior to the Early Termination Visit, a Post-Early Termination Safety Follow-Up Visit (Section 6.2.35) is not required.

1. If the Early Termination Visit coincides with previously planned scheduled visit for which a PD diary was completed, review the patient's PD diary recordings for the 3 consecutive days (i.e., 3 consecutive 24-hour periods) directly preceding this visit, and address any illegible or unclear entries.

Note: Efficacy-related measures (e.g., PD Diary) will not be completed at an Early Termination Visit during Part A if the subject stopped taking study drug more than 24 hours prior to the assessment of the measure.

- 2. Assess AEs by asking open-ended queries and record the assessments.
- 3. Record concomitant medication use; assess and record any changes to anti-PD medication dose or regimen.
- 4. Obtain weight.
- 5. Obtain and record BP and pulse measurements after at least 5 minutes supine rest and again after standing for approximately 1 and 3 minutes.

- 6. Obtain 12-lead ECG and ensure the ECG is collected at a time when the patient is not experiencing dyskinesia that would interfere with an adequate recording. Assess any changes from Baseline for clinical significance.
- 7. Perform physical and neurological examination, and assess any changes from Baseline for clinical significance.
- 8. Record the date and approximate time of the most recent dose of levodopa taken prior to the UPDRS assessment.
- 9. Perform the following assessments in the ON state (items a, b and c):

Note: Efficacy-related measures (e.g., UPDRS, CGI-I, PGI-I, and CGI-S) will not be completed at an Early Termination Visit during Part A if the subject stopped taking study drug more than 24 hours prior to assessment of the measure.

- a. Perform full UPDRS Parts I, II, III (motor) and IV, approximately 1 to 3 hours after the patient has taken a scheduled dose of levodopa (preferably their morning dose of levodopa). UPDRS in the ON state will be measured at a time representative of the ON state in that patient, not in "best" ON.

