7.0 ASSESSMENT OF EFFICACY

7.1 Hauser Parkinson's Disease Home Diary

During Screening and through Part A of the study, the Hauser Parkinson's Disease Home Diary will be completed on specified days directly preceding the scheduled study visits/assessments as outlined in the study procedures. Motor activity will be recorded as OFF, ON (mobility improved), or asleep time. Patients will be asked to record ON time according to dyskinesia categories "without dyskinesia", "with non-troublesome dyskinesia" or "with troublesome dyskinesia" (Hauser et al, 2000).

During Screening, patients (and/or caregivers) will be trained to complete a PD diary to record their status at half-hourly intervals as OFF, ON without dyskinesia, ON with non-troublesome dyskinesia, ON with troublesome dyskinesia, or asleep. The PD diary trainer/rater will emphasize the need for the patient to be consistent in their use of the definitions when rating their status in the PD diary during the study.

When instructions appear to have been understood by the patient (and caregiver, as applicable), a PD diary concordance session will be initiated during which the patient and trainer/rater will concurrently complete separate training diaries for at least 5 consecutive half-hour intervals (minimum 2.5 hours). During the diary concordance session, the patient must experience both ON and OFF. The 2.5 hour session may be extended, as needed, so that the patient experiences OFF. If the patient is OFF at the beginning of the diary concordance session, they may be administered their next dose of levodopa-containing medication in order to experience ON. When the session is completed, the trainer/rater will review and assess diary concordance between the patient and the trainer/rater. For the session, the patient is required to reach at least 80% overall diary concordance with the trainer/rater including at least 1 OFF interval. If the concordance criteria are not achieved, the trainer/rater will schedule a second PD diary training and diary concordance session within the 6-week Screening Period, unless the patient declines further participation.

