11.8 Handling of Dropouts or Missing Data

A valid diary will not have more than 2 hours (4 invalid entries) over a given 24-hour period. An invalid diary entry is defined as more than one entry recorded in a given half-hour interval, an unreadable entry, or the absence of an entry in a given half-hour interval. The average diary information from 3 valid diaries (if available) for each visit will be used to calculate diary-based efficacy endpoints. If there are only 2 valid diaries for a visit then the average information from the 2 valid diaries will be used. If only one diary is valid, information from the single valid diary

will be used. If no valid diaries are available for a patient visit then the diary information is considered missing.

For patients that prematurely withdrew from study, data collected during the Early Termination Visit will be used to impute 'OFF' time at the next visit. If the first diary day for a premature withdrawal visit was recorded more than one day after the last dose was administered, then the visit will not be used. The primary analysis of the primary efficacy variable will be based on an MMRM approach, hence visits beyond the Early Termination Visit will not to be imputed.

The total time 'OFF' will be determined by using the mean of the 3-day diary data immediately before each visit. A diary day will be regarded to be valid if at least 22 hours of the 24 hour clock are filled in. The missing hours will be imputed according to the proportions of being "on without dyskinesia", "on with troublesome dyskinesia", "on with non-troublesome dyskinesia", "off" and asleep. The visit data will be regarded to be valid if at least 2 days out of 3 are valid.

[figure not shown]

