9.6.1 Primary Variable

The primary variable, change from baseline to Week 24 in the 3-day average of total awake time in hours per day spent in the OFF state, will be summarized and analyzed in the mITT and repeated in the PPS.

Descriptive statistics (n, mean, standard deviation, median, minimum, and maximum) will be used to summarize results for OFF time by treatment group and week. Only valid diaries (see **Section 5.3**) post baseline are included in the analyses.

At Week 24, a plot of the cumulative distribution (cumulative of subjects) of average change from baseline in OFF state in hours will be displayed.

The null and alternative hypotheses are as follows:

 H_0 : $\mu_a - \mu_p = 0$

 H_1 : $\mu_a - \mu_p \neq 0$

where μ_a and μ_p are the mean changes from baseline to Week 24 in the 3-day average of total awake time in hours per day spent in the OFF state for the tozadenant and placebo groups, respectively.

The primary analysis will be performed on the change from baseline OFF hours using a mixed model repeated measures ANCOVA that includes fixed terms for country/region, treatment group, week (categorical: 2, 6 12, 18 and 24), interaction between treatment group and week, baseline number of hours of OFF time (covariate) and random effect for subject. This model will allow for estimation of treatment effects (each dose regimen of tozadenant vs placebo) separately at each week as well as averaged across weeks.

Restricted Maximum Likelihood (ReML) estimation will be used with an unstructured covariance structure to model the within-patient error and the Kenward-Roger approximation to estimate the

degrees of freedom. If the model does not converge using the unstructured covariance structure, the AR(1) structure may be considered.

MMRM model assumptions including constant variance, normality of errors and normality of random intercepts will be assessed by residual plots.

CONFIDENTIAL

A test of the null hypothesis of the equality of the adjusted group means in the tozadenant and placebo groups will be performed for each dose regimen of tozadenant using a significance level of 5% (two tailed). Treatment differences will be summarized by least squares means (standard errors) and corresponding 95% confidence intervals.

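### Protocol 11.8 contradicts itself on which visit an Early Termination diary belongs to, and the SAP has no rule that settles it

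*Protocol*

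**What the plan says.** - **Collection.** Protocol Table 1, footnote j, on the ET diary: "Done only if the ET date coincides with the scheduled diary collection return date". Section 6.2.32 agrees and has the diary reviewed under this condition: "If the Early Termination Visit coincides with previously planned scheduled visit for which a PD diary was completed".
- **Use in the analysis.** Protocol 11.8: "For patients that prematurely withdrew from study, data collected during the Early Termination Visit will be used to impute" OFF time at the next visit. Two sentences later, with the MMRM given as the reason: "hence visits beyond the Early Termination Visit will not to be imputed".
- **Withdrawal at Week 24.** Protocol 6.2.18: "If a patient decides to withdraw from study at Week 24, their Week 24 visit will be an Early Termination Visit". The synopsis and section 6.1 say the same.
- **Model.** SAP 9.6.1 fits week as a factor: "week (categorical: 2, 6 12, 18 and 24". Week 24 is the last level. Protocol 7.1 confines the diary to this period: "During Screening and through Part A of the study". Table 2 schedules no diary in Part B.
- **SAP on ET data.** SAP 9 imputes missing data only where the SAP itself documents a method. SAP 9.6.2 documents LOCF and multiple imputation. Neither section assigns an ET diary to a week.

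**The concern.** The rule does not fit the data it governs. An ET diary is not taken at an arbitrary time between visits; it exists only on a scheduled date and so has its own week. Sending it to the following visit moves a correctly dated observation. It also fills a week that, on the paragraph's own closing statement, should stay empty. Two programmers could follow section 11.8 in good faith and build different primary datasets.

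Week 24 is the sharpest case because it is the primary time point. A patient who withdraws there has a diary for the right days, but the visit is recorded as ET and no later Part A visit can receive it. If that diary were not placed at Week 24:

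- the MMRM would lack an observed Week 24 value;
- the patient could miss the Per Protocol Set, which requires a Week 24 evaluation;
- LOCF would carry an earlier value forward;
- the multiple imputation in SAP 9.6.2.2 could treat a tozadenant completer as a withdrawal and impute from placebo data.

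**Working it through.** **1. Literal mapping.** Inputs: the model weeks 2, 6, 12, 18 and 24 (SAP 9.6.1), the coincidence condition (Table 1 footnote j) and the next-visit rule (protocol 11.8).

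| ET diary collected for | Next week in the model | Shift |
|---|---|---|
| Week 2 | Week 6 | 6 − 2 = 4 weeks |
| Week 6 | Week 12 | 12 − 6 = 6 weeks |
| Week 12 | Week 18 | 18 − 12 = 6 weeks |
| Week 18 | Week 24 | 24 − 18 = 6 weeks |
| Week 24 | none | – |

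Each shift fills a week after the patient has left, and empties the observed week unless the same diary is used twice. Only the Week 18 row reaches the primary time point. The Week 24 row has no destination: Week 26 is a Part B visit, outside the Part A model and without a diary.

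**2. Against the closing sentence of the same paragraph.** In the first four rows the receiving week lies beyond the ET Visit, which section 11.8 says is not imputed. The two sentences cannot both be applied as plainly read.

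**3. Last-dose conditions.** Section 11.8 drops the visit if the first diary day falls more than one day after the last dose. Table 1 footnote x and section 6.2.32 drop the measure if drug stopped more than 24 hours before its assessment. The synopsis counts the 24 hours back from the ET Visit. The diary covers the three days before the visit. A patient whose last dose was two days before the visit began the diary while still on drug, so passes section 11.8 and fails the other conditions.

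**4. The plan's own power figure.** Inputs from protocol 11.10: n = 150 per arm, difference 0.9 h, SD 2.6 h, two-sided 0.05. Power ≈ Φ(δ / (σ√(2/n)) − 1.96).

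With n = 150: 2.6 × √(2/150) = 0.3002; 0.9 / 0.3002 = 2.998; Φ(1.038) = 85.0%. The noncentral t gives 84.8%. The stated 85% reproduces.

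**5. Illustration of size.** Protocol 3.1.2 expects 80% (360 of 450) to complete Part A and continue. The other 20% is not split into earlier dropouts and Week 24 withdrawals, so the shares below are assumptions. At 20%, 0.20 × 150 = 30 per arm.

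| Assumed share losing Week 24 | n left per arm | Power, Week 24 comparison alone |
|---|---|---|
| 2% | 147 | 84.3% |
| 5% | 142 | 83.1% |
| 10% | 135 | 81.2% |
| 20% (ceiling) | 120 | 76.5% |

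These are two-sample figures. They ignore what the MMRM recovers from Weeks 2 to 18.

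**The case against.** There is a coherent reading. Counted from the last completed visit, the next visit is the scheduled one that the ET Visit coincides with or replaces: a patient last seen at Week 12 who terminates on the Week 18 diary date goes to Week 18. This agrees with footnote j, section 6.2.32 and the closing sentence of section 11.8. It may be what was meant, but neither document says so, and for an ET Visit held on a scheduled date the plain reading is the following visit.

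The SAP also does not carry the next-visit rule. Under its default on missing data, the forward shift would not be run from the SAP alone. That stands, but SAP 1 asks to be read together with the protocol, and the SAP offers no placement of its own.

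Finally, nothing instructs anyone to discard a Week 24 ET diary. Section 6.2.18 still calls the visit that patient's Week 24 visit, the model term is week rather than visit code, and the Per Protocol Set asks for an evaluation at Week 24. This stands too. What remains is a labelling risk: Table 1 gives the ET Visit its own visit number, and SAP 9.7.4 summarises early termination separately from Week 24.

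A reader might infer that 5% to 20% of each arm will lose the primary value and that power falls to 76.5%. The documents do not support that. The 20% case needs no dropout before Week 24, every Week 24 withdrawal's diary discarded, and no recovery by the MMRM.

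**Conclusion.** The point holds as an internal inconsistency in a rule that governs primary-endpoint data. Followed literally, protocol 11.8 places an ET diary 4 to 6 weeks late, turns a Week 18 diary into the Week 24 value, and gives a Week 24 ET diary no slot. Followed by its closing sentence, it does none of the forward shifting. The SAP does not choose between the two.

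The size cannot be stated from the documents. The share of patients with an ET diary at Week 18 or Week 24 is not given; 20% is a ceiling on Week 24 withdrawals that also contains all earlier dropouts. The power table is an assumed range, not a forecast. The sample size and its 85% power are correct on their own inputs. It would also be too strong to say that the plan orders the loss of Week 24 data: that loss follows only if the ET label is taken to override the week.

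**What to change.** Replace the next-visit sentence in protocol 11.8, and add the same rule to SAP 9.6:

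1. An ET diary that meets the last-dose condition is analysed at the scheduled week for which it was collected.
2. A Week 24 visit recorded as ET is analysed as Week 24 in the MMRM, the Per Protocol Set, LOCF and multiple imputation.
3. No ET diary is moved to a later week.

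Reconcile the last-dose conditions for using an ET diary in protocol 11.8, Table 1 footnote x, section 6.2.32 and the synopsis, and state the result identically in both documents. Which condition applies is for the sponsor to decide.

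The cost is a few sentences in each document. The assignment rule needs no new data, visits or patients. It should be settled before Part A is unblinded, because protocol 11.6 and SAP 8 declare the primary and secondary analyses final.

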11.9 Planned Safety Data Monitoring

Concurrent safety data monitoring is planned for this study, for which responsibility will be assigned to an independent DSMB. The DSMB will oversee the safety of the study by reviewing relevant data on a regular basis. The DSMB will consist of members who are independent from Biotie Therapies. Study enrollment will not be halted during planned DSMB reviews of safety data. The objectives and procedures for the DSMB will be detailed in the DSMB charter.

11.10 Determination of Sample Size

The primary efficacy endpoint is the change from Baseline to Week 24 in the number of hours per day spent in the OFF state. A sample size of 150 in each group will provide 85% power to detect a difference in mean response of 0.9 hours between tozadenant and placebo assuming the common SD is 2.6 hours and using a two group t-test with a 0.050 two-sided significance level. Across the 3 treatment groups, the total number of patients to be randomized is 450.

Although the sample size calculation is based on the primary endpoint, OFF time, for this study the total sample size of 450 patients is anticipated to yield power to detect treatment differences

Approximately 645 patients will be screened, assuming a 30% screen failure rate, to randomize 450 patients.

12.0 ETHICS AND REGULATORY REQUIREMENTS

12.1 Informed Consent

Patient's informed consent must be obtained and documented in accordance with local regulations, ICH GCP requirements, and the ethical principles that have their origin in the principles of the Declaration of Helsinki.

Prior to obtaining informed consent, information should be given in a language and at a level of complexity understandable to the patient in both oral and written form by the investigator (or designee). Each patient will have the opportunity to discuss the study and its alternatives with the investigator.

Prior to participation in the study, the written ICF will be signed and personally dated by the patient, and by the person who conducted the informed consent discussion (investigator or designee). The patient must receive a copy of the signed and dated ICF. As part of the consent process, each patient must consent to direct access to his/her medical records for study-related monitoring, auditing, IRB/IEC review, and regulatory inspection.

If the ICF is amended during the study, the investigator (or the Sponsor, if applicable) must follow all applicable regulatory requirements pertaining to the approval of the amended ICF by the IRB/IEC and use of the amended ICF.

All studies conducted at centers in the United States must include the use of a Health Insurance Portability and Accountability Act (HIPAA) authorization form.

The patient may withdraw his/her consent to participate in the study at any time. A patient is considered to be in the study once they have signed the ICF. An eCRF must not be started, nor may any study-specific procedure be performed for a given patient, without having obtained the patient's written consent to participate in the study.

